- For sites at an altitude \leq 5000 feet: peripheral capillary oxygen saturation (SpO_2) \leq 93% or partial pressure of oxygen/fraction of inspired oxygen \leq 300 mmHg or requirement for supplemental oxygen to maintain SpO_2 $>$ 93%
- For sites at an altitude $>$ 5000 feet: requirement for supplemental oxygen to maintain SpO_2 at an acceptable level per local standard of care
- For women of childbearing potential: agreement to remain abstinent (refrain from heterosexual intercourse) or use contraception, as defined below:

Women must remain abstinent or use contraceptive methods with a failure rate of $< 1\%$ per year during the treatment period and for 95 days after the final dose of study drug.

A woman is considered to be of childbearing potential if she is postmenarchal, has not reached a postmenopausal state (≥ 12 continuous months of amenorrhea with no identified cause other than menopause), and is not permanently infertile due to surgery (i.e., removal of ovaries, fallopian tubes, and/or uterus) or another cause as determined by the investigator (e.g., Müllerian agenesis). The definition of childbearing potential may be adapted for alignment with local guidelines or regulations.

Examples of contraceptive methods with a failure rate of $< 1\%$ per year include bilateral tubal ligation, male sterilization, hormonal contraceptives that inhibit ovulation, hormone-releasing intrauterine devices, and copper intrauterine devices.

The reliability of sexual abstinence should be evaluated in relation to the duration of the clinical trial and the preferred and usual lifestyle of the patient. Periodic abstinence (e.g., calendar, ovulation, symptothermal, or postovulation methods) and withdrawal are not adequate methods of contraception. If required per local guidelines or regulations, locally recognized adequate methods of contraception and information about the reliability of abstinence will be described in the local Informed Consent Form.

- For men: agreement to remain abstinent (refrain from heterosexual intercourse) or use a condom, and agreement to refrain from donating sperm, as defined below:

With a female partner of childbearing potential or pregnant female partner, men must remain abstinent or use a condom during the treatment period and for 95 days after the final dose of study drug to avoid exposing the embryo. Men must refrain from donating sperm during this same period.

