2.1 EFFICACY OBJECTIVES

2.1.1 Primary Efficacy Objective

The primary efficacy objective for this study is to evaluate the efficacy of MSTT1041A compared with placebo and of UTTR1147A compared with placebo, in combination with SOC, on the basis of the following endpoint:

- *Time to recovery, defined as time to score of 1 or 2 on the 7-category ordinal scale (whichever occurs first)*

MSTT1041A/UTTR1147A—Genentech, Inc.
31/Protocol GA42469, Version 4

The ordinal scale categories are as follows:

1. Discharged (or “ready for discharge” as evidenced by normal body temperature and respiratory rate, and stable oxygen saturation on ambient air or ≤ 2 L supplemental oxygen)
2. Non-ICU hospital ward (or “ready for hospital ward”) not requiring supplemental oxygen
3. Non-ICU hospital ward (or “ready for hospital ward”) requiring supplemental oxygen
4. ICU or non-ICU hospital ward, requiring non-invasive ventilation or high-flow oxygen
5. ICU, requiring intubation and mechanical ventilation
6. ICU, requiring extracorporeal membrane oxygenation (ECMO) or mechanical ventilation and additional organ support (e.g., vasopressors, renal replacement therapy)
7. Death

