3.3.3 Rationale for Patient Population

Approximately 15%–20% of patients with COVID-19 pneumonia have severe disease requiring hospitalization and supplemental oxygen and 5% of patients with COVID-19 pneumonia will be admitted to the ICU (WHO 2020b). Risk factors for progression to severe COVID-19 pneumonia are common and include advanced age, cardiovascular disease, diabetes mellitus, chronic lung disease, and chronic kidney disease (Liang et al. 2020; Wu et al. 2020; Zhou et al. 2020). In a study of 138 hospitalized patients with COVID-19 pneumonia in China, 26% of patients required transfer to the ICU and 4.3% of patients died (Wang et al. 2020). In a second study of 1099 Chinese patients with

MSTT1041A/UTTR1147A—Genentech, Inc.
41/Protocol GA42469, Version 4

COVID-19 pneumonia, 5% of patients were admitted to the ICU, 2.3% of patients underwent invasive mechanical ventilation, and 1.4% of patients died (Guan et al. 2020). Patients with severe COVID-19 pneumonia requiring hospitalization and supplemental oxygen have significant morbidity and mortality and despite multiple experimental therapies in wide use, there are no treatments with proven efficacy to date. This study will enroll patients hospitalized with severe COVID-19 pneumonia requiring supplemental oxygen at high risk of developing ARDS, hypoxic respiratory failure and death.

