4.1.1 Inclusion Criteria

Patients must meet the following criteria for study entry:

- Documented informed consent as described in Section [4.5.1](#)
- Age ≥ 18 years at time of signing Informed Consent Form

MSTT1041A/UTTR1147A—Genentech, Inc.
42/Protocol GA42469, Version 4

- Ability to comply with the study protocol
- Hospitalized with COVID-19 pneumonia confirmed per WHO criteria (including a positive PCR of any specimen; e.g., respiratory, blood, urine, stool, other bodily fluid) and evidenced by chest X-ray or CT scan
- For sites at an altitude \leq 5000 feet: peripheral capillary oxygen saturation (SpO_2) \leq 93% or partial pressure of oxygen (PaO_2)/fraction of inspired oxygen (FiO_2) \leq 300 mmHg or requirement for supplemental oxygen to maintain $\text{SpO}_2 > 93\%$
- For sites at an altitude $>$ 5000 feet: requirement for supplemental oxygen to maintain SpO_2 at an acceptable level per local standard of care
- For women of childbearing potential: agreement to remain abstinent (refrain from heterosexual intercourse) or use contraception, as defined below:

Women must remain abstinent or use contraceptive methods with a failure rate of $< 1\%$ per year during the treatment period and for 95 days after the final dose of study drug.

A woman is considered to be of childbearing potential if she is postmenarchal, has not reached a postmenopausal state (≥ 12 continuous months of amenorrhea with no identified cause other than menopause), and is not permanently infertile due to surgery (i.e., removal of ovaries, fallopian tubes, and/or uterus) or another cause as determined by the investigator (e.g., Müllerian agenesis). The definition of childbearing potential may be adapted for alignment with local guidelines or regulations.

Examples of contraceptive methods with a failure rate of $< 1\%$ per year include bilateral tubal ligation, male sterilization, hormonal contraceptives that inhibit ovulation, hormone-releasing intrauterine devices, and copper intrauterine devices.

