4.5.9 Ordinal Scale Determination

Assessment of clinical status using a 7-category ordinal scale will be recorded *prior to dosing* at baseline on Day 1 and then again once daily every morning (ideally, between 8 a.m. and 12 p.m.) *at subsequent visits* during patient hospitalization. When possible, the patient should be assessed at approximately the same time each day. The ordinal scale categories are as follows:

1. Discharged (or “ready for discharge” as evidenced by normal body temperature and respiratory rate, and stable oxygen saturation on ambient air or ≤ 2 L supplemental oxygen)
2. Non-ICU hospital ward (or “ready for hospital ward”) not requiring supplemental oxygen
3. Non-ICU hospital ward (or “ready for hospital ward”) requiring supplemental oxygen
4. ICU or non-ICU hospital ward, requiring non-invasive ventilation or high-flow oxygen
5. ICU, requiring intubation and mechanical ventilation
6. ICU, requiring ECMO or mechanical ventilation and additional organ support (e.g., vasopressors, renal replacement therapy)
7. Death

In general, patients with oxygen saturation consistently $\leq 90\%$ should be considered for escalation to a higher clinical status category, while patients with oxygen saturation consistently $\geq 96\%$ should be considered for de-escalation to a lower category.

However, actual clinical status category should be recorded on the eCRF. Please refer to the additional guidance for investigators regarding assessment of clinical status using the 7-category ordinal scale.

Patients on supplemental oxygen should be evaluated at least daily and considered for reduction or discontinuation of oxygen support. Actual changes in level of support will be at the discretion of the clinician(s) treating the patient based on the patient's overall condition and may be dictated by other clinical and non-clinical considerations.

Normal body temperature is defined as oral, rectal, axillary, temporal, or tympanic temperature 36.1°C – 38.0°C . Normal respiratory rate is defined as 12–20 breaths per minute.

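### At sites at or below 5000 feet the entry criteria admit patients without an oxygen requirement, so some may already meet the primary recovery definition before dosing

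*Protocol*

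**What the plan says.** **Population.** Protocol Section 3.3.3: "This study will enroll patients hospitalized with severe COVID-19 pneumonia requiring supplemental oxygen at high risk of developing ARDS".

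**Entry.** Above 5000 feet, Section 4.1.1 makes oxygen mandatory: "5000 feet: requirement for supplemental oxygen to maintain" an acceptable saturation. At or below 5000 feet it lists three alternatives: SpO2 ≤ 93%, PaO2/FiO2 ≤ 300, and only as the third "mmHg or requirement for supplemental oxygen to maintain" SpO2 above 93%. The synopsis has the same construction ("or partial pressure of oxygen/fraction of inspired oxygen" and so on). The exclusion criteria in Section 4.1.2 do not mention the ordinal score.

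**Endpoint.** Sections 2.1.1 and 6.4.1: "Time to recovery, defined as time to score of 1 or 2 on the 7-category ordinal scale (whichever occurs first". Category 2 is a non-ICU ward patient with no need for oxygen. Category 1 includes readiness for discharge with "stable oxygen saturation on ambient air or ≤ 2 L supplemental oxygen".

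**Scoring.** Under Section 4.5.9 the first score is taken before dosing on Day 1 and the actual category is recorded. Patients with saturation consistently at or below 90% "should be considered for escalation to a higher clinical status category". The section also points to "additional guidance for investigators regarding assessment of clinical status using the 7-category ordinal scale", which is a separate document.

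**Analysis set.** Section 6 defines mITT as all randomized patients who received a dose, with no exclusion by baseline score.

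**The concern.** The stated population and the operative criteria differ, and the difference falls on the boundary that defines the primary event. A ward patient breathing room air at SpO2 91–93% satisfies the first entry alternative, lies above the level at which escalation is prompted, and may be recorded as category 2 before the first dose. As written, the endpoint then counts that patient as recovered before treatment begins. Such a patient carries no information on the treatment effect on recovery, so the trial would be less sensitive than its sample size suggests.

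Other endpoints in Section 2.1.2 do allow for baseline status. The two-category improvement is measured from baseline, and clinical failure has its own rule for patients already in ICU or ventilated. The primary endpoint has no such provision.

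**Working it through.** **1. Can it happen?** Entry at or below 5000 feet is A or B or C, with an oxygen requirement only in C. A room-air ward patient at 91–93% meets A, and no exclusion refers to the score. Category 2 is open to that patient, and a score of 2 is the event. The mITT definition keeps the patient once dosed. The text therefore permits the sequence but does not dictate it.

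The PaO2/FiO2 alternative adds little. Footnote n of Appendix 1 schedules blood gases at screening and Day 1 only for mechanically ventilated patients with an arterial line. Historic standard-of-care values remain possible, but on room air the limit would need PaO2 ≤ 300 × 0.21 = 63 mmHg.

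**2. Inputs (Sections 6.1 and 6.4).** There are 390 patients at 2:2:1:1 with placebos pooled, so each comparison is 130 vs 130. Medians are 21 days on placebo and 14 on active (7-day difference), follow-up is 28 days, and alpha is one-sided 5%. My assumptions are exponential times (hazard ratio 21/14 = 1.5) and an unstratified test. The share f of patients scored 1 or 2 before dosing is not in the protocol; 5% and 10% are illustrative.

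**3. The plan's own figure.** The probability of an event by Day 28 is F(m) = 1 − exp(−ln2 × 28/m), so F(21) = 0.603 and F(14) = 0.750. Expected events are 130 × (0.603 + 0.750) = 175.9. Then z = ln(1.5) × √(175.9/4) = 2.689 and power = Φ(2.689 − 1.645) = 85.2%. Section 6.1 states approximately 80%. The difference is in the conservative direction and may be an unstated allowance; nothing below depends on it.

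**4. Power with a share f.**

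- d = 130(1 − f)[F(mP) + F(mT)] events after baseline, V1 = d/4.
- Left out of the risk set: z = ln(1.5) × √V1.
- Counted at time zero: D = 260f tied events add V0 = 0.25 × D(260 − D)/259 to the variance and nothing to the expected difference, so z = ln(1.5) × V1/√(V0 + V1).
- Reading A: medians 21/14 hold among patients not yet recovered at baseline.
- Reading B: they hold in the whole mITT set. Medians among the rest are then t × ln2/ln(2(1 − f)), that is 22.7/15.1 at 5% and 24.8/16.5 at 10%.

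| f | Reading | d | V0 | Left out | Time zero |
|---|---|---|---|---|---|
| 0 | – | 176 | 0 | 85% | 85% |
| 5% | A | 167 | 3.10 | 84% | 81% |
| 5% | B | 160 | 3.10 | 82% | 80% |
| 10% | A | 158 | 5.87 | 82% | 77% |
| 10% | B | 144 | 5.87 | 79% | 73% |

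Worked line, f = 10%, reading A: V1 = 158.3/4 = 39.58. Left out, z = 0.4055 × √39.58 = 2.551. At time zero, z = 0.4055 × 39.58/√(5.87 + 39.58) = 2.380.

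Simulation with a daily log-rank test (8,000 trials per cell) agreed within about one percentage point: left out 82.0–83.6% and 79.1–81.6%; time zero 79.2–80.6% and 72.2–76.8%.

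**5. Type I error.** Under the null (10,000 trials per cell, f = 0, 10 and 20%), one-sided error was 4.7–5.2% under either way of counting.

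**The case against.** - **Few such patients may exist.** Many clinicians would give oxygen at SpO2 ≤ 93%. Category 2 turns on not requiring oxygen, and the third entry alternative ties the requirement to keeping SpO2 above 93%, so category 3 is at least as natural a score at 91–93%. The site scoring guidance, not available here, may settle it. This stands, and it is why every figure is conditional on f.
- **The Data Analysis Plan may say how baseline scores of 1 or 2 are counted.** Sections 6.4 and 6.4.1 defer details to it, and it was not available. This also stands: the time-zero losses arise only if the patients are counted that way. But that plan cannot change who is randomized, and the left-out loss remains.
- **Section 3.3.3 is only a rationale.** True, and Section 4.1.1 and the synopsis agree with each other. The protocol still describes one population and admits another.
- **These patients are not worthless.** They can still inform clinical failure, clinical status at Days 14 and 28, ventilation and mortality. Excluding them has a price.

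A reader might infer that the trial falls well short of its stated 80% power, for example by scaling the calculation down so that f = 0 gives 80%. The protocol does not support this. The gap between 85% and 80% is unexplained, and if it is an allowance for loss it could already cover uninformative patients, so scaling would count the loss twice.

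**Conclusion.** The point holds as a faulty stated rule with a modest and uncertain cost. The primary event has no baseline condition, and the entry criteria at or below 5000 feet do not enforce the oxygen requirement that Section 3.3.3 describes. Followed as written, the plan can count a patient as recovered before dosing.

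The harm is lost sensitivity only. A reader might infer biased arms or false positives, but the score precedes dosing and affects the arms alike, and simulated error stays near 5%. A reader might also infer that every room-air patient will be scored 2; the text allows that score without requiring it.

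If affected patients are left out, power still meets or nearly meets the stated 80% at both illustrative shares. Counting them at time zero at f = 10% takes it clearly below. These results assume exponential times, a hazard ratio of 1.5 among patients not yet recovered, and an f that only the trial's data can supply.

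**What to change.** 1. Reconcile Section 3.3.3 with Section 4.1.1 and the synopsis so that entry and the primary endpoint are compatible, for example by requiring an ordinal score of 3 or higher recorded before randomization. Appendix 1 has no ordinal score at screening and footnote p says only that it precedes dosing, so the timing must be stated.
2. State in Sections 2.1.1 and 6.4.1 that the primary time-to-recovery analysis counts post-baseline scores of 1 or 2 in patients with a baseline score of 3 or higher, with full mITT as a sensitivity analysis. Fix this before unblinding, after a blinded pooled count of baseline scores, which Section 6.3 already summarizes.
3. Reconcile the scoring boundary between categories 2 and 3 for room-air patients at 91–93%, and between categories 1 and 3 for patients on ≤ 2 L oxygen (Sections 2.1.1 and 4.5.9). The entry condition alone does not prevent a 3 at entry and a 1 or 2 the next morning. No clinical or scoring rule is proposed here.

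**Cost.** An amendment with the approvals in Section 9.6, slightly narrower entry, patients enrolled under two versions of the criteria, a primary set smaller than mITT by the share f, and the loss of secondary-endpoint information from patients no longer enrolled. No new type of data is needed. Reaching 390 patients with a score of 3 or higher takes 390/(1 − f) patients who meet the present criteria: 411 at f = 5%, 434 at 10%. With 390 so enrolled, power would be 84–85% and 82–85% respectively, provided the next-morning shift in item 3 does not occur.

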2.1.2 Secondary Efficacy Objective

The secondary efficacy objective for this study is to evaluate the efficacy of MSTT1041A compared with placebo and of UTTR1147A compared with placebo, in combination with SOC, on the basis of the following endpoints:

- Time to improvement of at least 2 categories relative to baseline on a 7-category ordinal scale of clinical status
- Time to hospital discharge or “ready for discharge” (as evidenced by normal body temperature and respiratory rate, and stable oxygen saturation on ambient air or ≤ 2 L supplemental oxygen)
- Duration of supplemental oxygen
- Proportion of patients alive and free of respiratory failure (requiring non-invasive ventilation, high-flow oxygen, mechanical ventilation, or ECMO) at Day 28
- *Clinical status assessed using a 7-category ordinal scale at Days 14 and 28*
- Incidence of *invasive* mechanical ventilation or ECMO
- Ventilator-free days to Day 28
- Incidence of ICU stay
- Duration of ICU stay
- Time to clinical failure, defined as the time to death, mechanical ventilation, ICU admission, or withdrawal of care (whichever occurs first). For patients entering the study already in ICU or on mechanical ventilation, clinical failure is defined as a one category worsening on the ordinal scale, withdrawal, or death.
- Mortality rate at Days 14 and 28
- Time to clinical improvement, defined as a National Early Warning Score 2 (NEWS2) of ≤ 2 maintained for 24 hours

2.1.3 Exploratory Efficacy Objective

The exploratory efficacy objective for this study is to evaluate the efficacy of MSTT1041A compared with placebo and of UTTR1147A compared with placebo, in combination with SOC, on the basis of the following endpoints:

- Incidence of vasopressor use
- Duration of vasopressor use
- Incidence of starting hemodialysis
- SARS-CoV-2 viral load on Day 15 and Day 28
- Proportion of patients with secondary bacterial infections

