Patients who do not meet the criteria for participation in this study (screen failure) may qualify for one re-screening opportunity (for a total of two screenings per participant) at the investigator's discretion. The investigator will record the reasons for screen failure in the screening log (see Section 4.5.1).

[figure not shown]
Patients who are eligible to be re-screened will be required to repeat assessments as follows:

- Within the 2-day screening window: Repeat only the assessments that triggered screen failure.
- Outside the 2-day screening window: Repeat all assessments. The consent process does not need to be repeated if re-screening is completed within 7 days after completion of initial informed consent.

Note: Historic standard of care test results are acceptable for CT scan or chest X-ray if performed within 7 days prior to randomization, and for influenza and SARS-CoV-2 virology if performed within 14 days of randomization (see [Appendix 1](#)).

[Figure 1](#) presents an overview of the study design. A schedule of activities for patients in the hospital is provided in [Appendix 1](#). A schedule of activities for patients who will be discharged from the hospital *or transferred to a different care facility* prior to Day 60 is provided in [Appendix 2](#).

Figure 1 Study Schema

PBO=placebo; SOC=standard of care.

Screening period will be up to 2 days.

A second dose of study drug will be given on Day 15 if the patient remains hospitalized with a requirement for supplemental oxygen therapy, unless the patient meets the study drug discontinuation criteria (see Section 4.6.1).

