- Nasopharyngeal swabs for SARS-CoV-2 central virology tests (viral load and exploratory analysis)

Exploratory biomarker research may include, but will not be limited to, analysis of sST2, IL-22, IL-22 binding protein (IL-22BP), CRP, and REG3A, inflammatory mediators, and ARDS-related variables.

Research may involve extraction of RNA and genomic profiling through use of next-generation sequencing (NGS) of a comprehensive panel of genes.

For sampling procedures, storage conditions, and shipment instructions, see the laboratory manual.

Biological samples will be destroyed no later than the time of completion of the final Clinical Study Report, with the following exceptions:

- Serum samples collected for PK or immunogenicity analysis may be needed for additional immunogenicity characterization and for PK or immunogenicity assay development and validation and biomarker measurements; therefore, these samples will be destroyed no later than 15 years after the final Clinical Study Report has been completed.
- Serum, blood PAXgene, and fluid samples (nasopharyngeal swabs, if applicable) collected for biomarker research will be destroyed no later than 15 years after the final Clinical Study Report has been completed. However, the storage period will be in accordance with the IRB/EC-approved Informed Consent Form and applicable laws (e.g., health authority requirements).

When a patient withdraws from the study, samples collected prior to the date of withdrawal may still be analyzed, unless the patient specifically requests that the samples be destroyed or local laws require destruction of the samples. However, if samples have been tested prior to withdrawal, results from those tests will remain as part of the overall research data.

Data arising from sample analysis including data on genomic variants will be subject to the confidentiality standards described in Section [8.4](#).

MSTT1041A/UTTR1147A—Genentech, Inc.
53/Protocol GA42469, Version 4

Given the complexity and exploratory nature of exploratory biomarker analyses, data derived from these analyses will generally not be provided to study investigators or patients unless required by law. The aggregate results of any conducted research will be available in accordance with the effective Sponsor policy on study data publication.

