6.4 EFFICACY ANALYSES

Efficacy analyses will be conducted on the mITT population, consisting of all patients randomized in the study who received at least one dose of study drug, with patients grouped according to the treatment assigned at randomization.

MSTT1041A/UTTR1147A—Genentech, Inc.
81/Protocol GA42469, Version 4

MSTT1041A placebo and UTTR1147A placebo will be pooled in efficacy analyses. Comparison of efficacy will be performed between each of the two treatment groups and the pooled placebo. That is, there are two comparisons:

- MSTT1041A with pooled placebo
- UTTR1147A with pooled placebo

Sensitivity analyses to evaluate the robustness of results will be conducted with comparison of primary efficacy endpoint between MSTT1041A and MSTT1041A placebo, and between UTTR1147A and UTTR1147A placebo.

Details on analysis methods, sensitivity analyses, hypothesis testing, and type I error control across treatment groups will be specified in the Data Analysis Plan (DAP).

Unless otherwise noted, analyses of efficacy outcome measures will be adjusted by stratification factors (the need for invasive mechanical ventilation [yes vs. no] and region).

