Appendix 1: Schedule of Activities (Inpatients Only)

	SCR ^{cc}	Baseline	Primary Phase																								Follow up	SC ^a				
Study day	-2 to RAND	1	2	3	4	5	6	7	8	9	10	11	12	13	14	15	16	17	18	19	20	21	22	23	24	25	26	27	28	35	45	60 or ED
Visit window		0	b	b				b		b					c		b			b								b	±2 D	±2 D	±3 D	
Adverse events ^u		X	X	X	X	X	X	X	X	X	X	X	X	X	X	X	X	X	X	X	X	X	X	X	X	X	X	X	X	X		
Concomitant medications ^v		X	X	X	X	X	X	X	X	X	X	X	X	X	X	X	X	X	X	X	X	X	X	X	X	X	X	X	X			
Study drug administration		X													X ^w																	
CENTRAL LABS																																
Serum PK sample(s) ^x		X	X	X				X							X					X ^y							X			X		
Serum ADA sample ^z		X														X												X			X	
Serum sample for biomarkers ^z		X	X	X				X							X				X ^y								X			X		
Blood in PAXgene [®] tubes for biomarkers ^z		X		X			X																					X				
SARS-CoV-2 viral load ^{aa}		X													X				X ^y								X					
Blood sample for WGS (optional) ^{bb}		X																														

MSTT1041A/UTTR1147A—Genentech, Inc.
102/Protocol GA42469, Version 4

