- ^c It is preferred that the second dose of study drug be administered on Day 15. In cases where this is not possible, study drug administration can occur on Day 14, Day 16, or Day 17, provided a pregnancy test (women of childbearing potential), ECG, vital signs, hematology, chemistry, coagulation, NT-proBNP or BNP, troponin I or T, and CRP are performed and evaluated within 2 days prior to study drug administration. Samples for central laboratory tests must also be collected prior to study drug administration, with the exception of the post-dose PK sample.
- ^d Informed consent must be documented before any study-specific screening procedure is performed.
- ^e For screening, historic results of influenza and SARS-CoV-2 virology, performed within 14 days prior to Day 1 are acceptable.
- ^f Medical history, including clinically significant diseases, surgeries, cancer history (including prior cancer therapies and procedures), reproductive status, smoking history, and home oxygen use will be recorded at screening.
- ^g Physical examination includes evaluation of the head, eyes, ears, nose, and throat, and the cardiovascular, dermatologic, musculoskeletal, respiratory, gastrointestinal, and neurologic systems.
- ^h If weight or height cannot be assessed on the indicated study day, the most recent documented value is acceptable (e.g., from hospital admission).
- ⁱ Assessment is optional (to be performed at the investigator's discretion) for patients who will not receive a second dose.

MSTT1041A/UTTR1147A—Genentech, Inc.

103/Protocol GA42469, Version 4

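### The stated default for SARS-CoV-2 viral load on Days 15 and 28 does not use the Day 1 value of the same assay, which costs precision but causes no bias

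*Protocol*

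**What the plan says.** Section 2.1.3 of the protocol defines the endpoint as a level: "SARS-CoV-2 viral load on Day 15 and Day 28". Elsewhere the protocol says so when it means a comparison with baseline, as in the two-category improvement endpoint (Section 2.1.2) and the safety endpoints (Section 2.2).

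The measurement comes from one site of the body. Section 4.5.6 lists, among centrally analysed samples, "Nasopharyngeal swabs for SARS-CoV-2 central virology tests (viral load and exploratory analysis". Appendix 1 marks the viral load sample as mandatory at baseline (Day 1).

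Entry is broader. Section 4.1.1 requires confirmed COVID-19 pneumonia, "including a positive PCR of any specimen; e.g., respiratory, blood, urine, stool, other bodily fluid". On timing, Section 3.1.1 accepts historic results "for influenza and SARS-CoV-2 virology if performed within 14 days of randomization", and footnote e of Appendix 1 agrees: "historic results of influenza and SARS-CoV-2 virology, performed within 14 days prior to Day 1 are acceptable".

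For analysis, Section 6.4 sets a default that "analyses of efficacy outcome measures will be adjusted by stratification factors", naming need for invasive mechanical ventilation and region, unless something else is noted. Section 6.4.2 applies those covariates to the secondary endpoints in mITT, and Section 6.4.3 extends the secondary methods to exploratory endpoints where they fit. Section 6.4.2 leaves the full methods and missing-data handling to the Data Analysis Plan (DAP).

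**The concern.** The entry specimen and the endpoint specimen need not match. A patient can qualify on a stool, urine or blood result, or on a swab up to two weeks old, and have little or no nasopharyngeal virus when dosed. Day 1 nasopharyngeal load will therefore differ widely between patients for reasons unrelated to treatment. If it predicts later load, a model without it carries avoidable residual variance.

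The protocol is not silent here: it names a covariate set and a population for this endpoint, and the named set omits the pre-dose value of the same measurement, which is collected anyway. What is at stake is the precision of an exploratory comparison. It has some bearing on Section 1.4.1, which hypothesises that MSTT1041A can act without impairing viral clearance. An imprecise comparison could miss a difference in either direction. That rationale concerns one of the two drugs.

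**Working it through.** The protocol states no standard deviation, effect, power or detection limit for viral load, so there is no figure to reproduce. The check is an illustration over assumed ranges.

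**Inputs from the protocol.** About 390 patients at 2:2:1:1 (Section 6.1), placebos pooled (Section 6.4): 390 × 2/6 = 130 per active arm and 390 × (1 + 1)/6 = 130 on pooled placebo.

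**Assumed inputs.**
- f: share with no detectable nasopharyngeal virus on Day 1, taken to show no treatment effect; 0 to 40%.
- ρ: correlation of Day 1 with later log10 load; 0.3 to 0.7. ρ = 0 stands for no Day 1 adjustment.
- d: effect among detectable patients in SD units, set to give 80% power at f = 0, ρ = 0, two-sided 5%: d = (1.960 + 0.842) × √(2/130) = 0.347.
- Everyone sampled.

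**Formula.** Power = Φ( d(1 − f) / [√(1 − ρ²) × √(2/130)] − 1.960 ). Since d/√(2/130) = 2.802, this is Φ( 2.802(1 − f)/√(1 − ρ²) − 1.960 ).

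Example, f = 20%. Unadjusted: 2.802 × 0.8 = 2.241, and Φ(2.241 − 1.960) = 61%. With the Day 1 value at ρ = 0.5: 2.241/0.866 = 2.588, and Φ(2.588 − 1.960) = 74%.

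| f | no Day 1 value | ρ = 0.3 | ρ = 0.5 | ρ = 0.7 |
|---|---|---|---|---|
| 0% | 80.0% | 83.6% | 89.9% | 97.5% |
| 10% | 71.3% | 75.3% | 82.9% | 94.2% |
| 20% | 61.1% | 65.2% | 73.5% | 88.1% |
| 40% | 39.0% | 42.2% | 49.2% | 65.3% |

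Reading down a column shows dilution, which follows from who is enrolled; a covariate does not remove it. Reading across a row shows what the analysis choice costs. Residual variance is multiplied by 1 − ρ² = 0.91, 0.75 or 0.51, so omitting the Day 1 value is like needing 1/0.91 = 1.10, 1/0.75 = 1.33 or 1/0.51 = 1.96 times as many patients.

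**Simulation with an explicit assay floor.** Assumptions: 130 per group, floor 2 log10, baseline mean 5 (SD 1.3) log10 when detectable, mean fall 2 log10, true difference 0.5 log10 where measurable, one-sided 5%, everyone sampled. With 0, 10, 20 and 40% undetectable on Day 1:

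| Correlation among detectable | Power, unadjusted | Power, with Day 1 value |
|---|---|---|
| 0.3 | 90, 84, 77, 62% | 92, 89, 85, 76% |
| 0.6 | 89, 84, 77, 59% | 97, 95, 93, 85% |

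The direction is the same. Part of the gain is built in, because undetectable patients are held at the floor at both visits: in the 0.3 case the whole-sample correlation is about 0.41, 0.49 and 0.61 at 10, 20 and 40% undetectable.

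**Restricting to Day-1-detectable patients.** Under the same assumptions, restriction plus covariate against covariate alone in everyone gives 86% against 86% (20% undetectable, correlation 0.3), 76% against 76% (40%, 0.3) and 85% against 85% (40%, 0.6). Restriction adds no power.

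**The case against.** The strongest reply is that this is DAP content. A baseline covariate and a detection-limit rule for one of five exploratory endpoints are routinely settled there, and the protocol defers methods to it. Most of this stands and is why the point is minor. What remains is that the protocol states a default covariate set and population, and that default can be improved at no cost.

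Several stronger readings are tempting, and the documents do not support them.

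- A reader might infer that viral load will be analysed without its Day 1 value. No text excludes it. The Section 6.4 default allows for exceptions, Section 6.4.3 applies the secondary methods only where they suit, and a mandatory Day 1 sample is consistent with an intention to use it.
- A reader might infer that Day 1 load is the strongest covariate available. No figure in the protocol ranks covariates.
- A reader might infer that the comparison is distorted. It is a randomised comparison in all dosed patients; neither mechanism biases it under the null or raises type I error. No power is claimed for this endpoint, so no stated target is missed.
- A reader might infer that the main analysis should be confined to patients detectable on Day 1. That departs from mITT, gains no power in the check above, and drops patients who could later turn positive, a signal that matters if impaired clearance is the worry.

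The illustration also overstates the sample. Under Appendix 2, patients discharged on or before Day 15 have a discharge-day swab and no Day 15 swab, and Day 28 is in clinic only if possible. Fewer than 130 per group will contribute.

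**Conclusion.** The point holds as a small precision gain over the stated default for an exploratory endpoint. Viral load on Days 15 and 28 is by default adjusted for ventilation and region in mITT, while a mandatory Day 1 value of the same nasopharyngeal assay goes unmentioned, in a population whose Day 1 load will vary because of the entry rule.

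The direction is secure if Day 1 load is correlated with later load. The size is unknown: f, ρ, the SD and the effect are all assumptions. Validity is not in question, and the primary and secondary endpoints are untouched.

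**What to change.** Add to Section 6.4.3 that viral load at Day 15 and Day 28 is analysed in mITT with Day 1 nasopharyngeal log10 viral load as a covariate in addition to the stratification factors, and that values below the detection limit are treated as left-censored. Say also how an undetectable Day 1 value enters as a covariate, for example set at the limit with an indicator. Show the Day-1-detectable subset as a supportive analysis only. The endpoint wording in Section 2.1.3 can stay.

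The cost is wording: the Day 1 sample is already mandatory and no patient or visit is added. The choice should be recorded before unblinding, so that neither the covariate nor the subset can appear to have been picked after seeing results.
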